4.1 Description of protocol design

4.1.1 Phase 0

In the proposed trial, patients will be administered ribociclib+everolimus prior to surgical resection of their tumor. Recurrent GBM patients will be randomized into one of the three time-interval cohorts for the first two dose levels.

In the lead-in dose escalation study, the first six subjects (lead-in) will receive ribociclib 400 mg and everolimus 2.5 mg orally-administered in 5 daily doses with the last dose. If one or less patient experiences DLT among the 6 patients, this regimen with ribociclib 400 mg and everolimus 2.5mg will be considered safe and we will continue with the dose escalation phase of the study up to Level 6.

Four dose escalation levels:

Level 0: ribociclib 400mg and everolimus 2.5

Level 1: ribociclib 600mg and everolimus 2.5mg

Level 2: ribociclib 600mg and everolimus 5mg

Level 3: ribociclib 600mg and everolimus 10mg

Level 4: ribociclib 600mg daily for 5 days and everolimus 50mg given once on Day 5.

Level 5: ribociclib 600mg daily for 5 days and everolimus 60mg given once on Day 5.

Level 6: ribociclib 600mg daily for 5 days and everolimus 70mg given once on Day 5.

Three to fourteen (3-14) patients will be enrolled into each level to observe AEs and DLTs. Detailed DLTs definition will be summarized in [Table 9](#).

All patients will receive ribociclib and everolimus orally-administered in 5 daily doses.

Cohort 1: last ribociclib+everolimus dose 1 to 3 hours prior to craniotomy for tumor resection (n=8 patients)

Cohort 2: last ribociclib+everolimus dose 7 to 9 hours prior to craniotomy for tumor resection (n=8 patients)

Cohort 3: last ribociclib+everolimus dose 23 to 25 hours prior to craniotomy for tumor resection (n=8 patients)

In Dose Level 0 three to six patients will be enrolled into the time interval cohorts, sequentially whenever possible (e.g. cohort 1, cohort 2, cohort 3, cohort 1...), with at least 1 patient in each of the time intervals.

In Dose Level 1

Three to six patients will be enrolled into the time interval cohorts, sequentially whenever possible (e.g. cohort 1, cohort 2, cohort 3, cohort 1...), with at least one patient in time cohort 1 and two patients in cohort 2. If there are positive PK/PD results at the Maximum Tolerated Dose (MTD) or Optimal Biological Dose (OBD) dose level, the dose level will be expanded to 8 additional patients with 4 patients in each time cohort 1 and 3 (Sections [6.1.2](#) and [6.1.2.1](#)).

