In Dose Levels 2+, three to six patients will be enrolled into cohort 2. If there are positive PK/PD results at the Maximum Tolerated Dose (MTD) or Optimal Biological Dose (OBD) dose level, the dose level will be expanded to 8 additional patients with 4 patients in each time cohort 1 and 3 (Sections [6.1.2](#) and [6.1.2.1](#)).

Dose Level	Time Interval	N=	Dose Expansion Cohort N=	Time Cohort Expansion N=
Level 0	Cohort 1	2	N/A	N/A
	Cohort 2	2		
	Cohort 3	2		
Level 1	Cohort 1	1	0	4
	Cohort 2	2	3	0
	Cohort 3	0	0	4
Level 2	Cohort 1	0	0	4
	Cohort 2	3	3	0
	Cohort 3	0	0	4
Level 3	Cohort 1	0	0	4
	Cohort 2	3	3	0
	Cohort 3	0	0	4
Level 4 - 6	Cohort 1	0	0	4
	Cohort 2	3	3	0
	Cohort 3	0	0	4

To assess the PK and PD endpoints listed above, blood, CSF and brain tumor tissue will be collected intraoperatively (enhancing and non-enhancing tumor tissue will be collected and analyzed separately).

Additionally, blood samples will be obtained on Day 4 in Dose Levels 1-3 (the day before the surgery for Cohorts 1 & 2; 2 days before surgery for Cohort 3) at pre-dosing (trough level), 0.5, 1, 2, 4, 7, and 24 hours post dose. (Note: 24 h sample is the pre-dosing (trough level) blood sample on Day 5).

Dose Level 4+ only: PK blood sampling will occur on Day 5: pre, 0.5, 1, 2, 4, 6, 8 and 24 hours post-dose (Note: 24 h sample is the pre-dosing (trough level) blood sample on Day 6).

Dose Levels 0-3:

[figure not shown]
PHASE 0 STUDY COHORT 1										
DAY 4 PRE- DOSE	Time 0	30 min	1 hour	2 hours	3 hours	4 hours	7 hours	24 hours ± 1 h	POSTOP- Phase 2	
Blood			Blood	Blood	Blood		Blood	Blood	Blood	
DAY 5 PRE- DOSE	Ribociclib + everolimus								Ribociclib + everolimus	
Blood			Blood* CSF* Tumor*							

PHASE 0 STUDY COHORT 2										
DAY 4 PRE- DOSE	Time 0	30 min	1 hour	2 hours	4 hours	7 Hours	8-9 Hours	24 hours ± 1 h	POSTOP- Phase 2	
Blood			Blood	Blood	Blood	Blood	Blood		Blood	
DAY 5 PRE- DOSE	Ribociclib + everolimus								Ribociclib + everolimus	
Blood			Blood* CSF* Tumor*							

PHASE 0 STUDY COHORT 3										
DAY 4 PRE- DOSE	Time 0	30 min	1 hour	2 hours	4 hours	7 Hours	23 -25 hours	POSTOP- Phase 2		
Blood	Ribociclib + everolimus		Blood	Blood	Blood	Blood	Blood	Blood	Ribociclib + everolimus	

Initial Version date: 10/16/2018

Revision date: 03/11/2019, 5/07/2019, 09/26/2019, 03/17/2020, 08/26/2024

[figure not shown]

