2	Screening assessment may be completed at Day 1 predose, if completed at screening, does not need to be repeated at Day 1 pre-dose except for ECG and ECOG. Results must be available to confirm eligibility prior to dosing.											
3	Estimated glomerular filtration rate (eGFR)											
4	ECG Day 1 Pre-dose, Day 1: 2-4 hrs post-dose, and pre-surgical assessment (can be completed on Day 4 or Day 5 (Cohort 1&2) / Day 6 (Cohort 3)).											
5	ECG Pre-dose and 2-4 hours post dose on C1D15, C2D15, C3D1, C6D1; C9D1; and every 3 rd cycle...											
6	ECG Pre-dose C2D1, C4D1, C5D1; C7D1, C8D1, C10D1, C11D1; and every 1st and 2nd cycle...											
7	Performed at pre-surgical assessment as per SOC on Day 4 (can be completed on Day 5 (Cohort 1&2) or Day 6 (Cohort 3)).											
8	Lipid panel performed every 4th cycle D1											
9	Study drugs are administered in the clinics on D1, D4 and D5. Patients may take medications at home on D2 and D3											
10	Trough blood sample is collected prior to the drug administration on that day. Study drugs are administered in the clinics on the clinic visit days 1, 8, 15, 22.											
11	Blood samples will be obtained on Day 4 (the day before the surgery for Cohorts 1 & 2; 2 days before surgery for Cohort 3) at pre-dosing (trough level), 0.5, 1, 2, 4, 7 hours post dose (\pm 5 min window for 0.5hr and 1hr; \pm 15min window for 2, 4, 7hr samples). A pre-dosing (trough level) blood sample will also be obtained on Day 5 and a sample will be collected intra-operatively. In Dose Level 4+ only, PK blood sampling will occur at the same timepoints (pre, 0.5, 1, 2, 4, 6, 8 and 24) but will be obtained on Day 5 (the day of surgery); the 24 hour sample will be obtained on Day 6.											
12	Only Patients that have a recurrence and undergo an additional surgery for tumor resection											
13	The start of follow up for long-term survival begins following completion of the Day 30 safety follow up call. Subjects will continue to be followed until death or withdrawal of consent for the collection and reporting of data or lost to follow-up for up to 5 years. Public records may be used to collect survival data, i.e., obituary notices and public database searches for survival information.											

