7.1.1.2 Pharmacometabolomics

Rationale: Novel metabolomics technologies allow high-throughput assessment of a large number of endogenous metabolites, which provide powerful tools for mapping biochemical pathways implicated in disease and in response to drug treatment. Pharmacometabolomics is an emerging field that applies metabolomics to define metabolic signature of drug exposure, thereby enabling identification of biochemical pathways implicated in drug efficacy and adverse drug reactions. By defining metabolite profiles both at baseline (prior to) and post drug exposure, pharmacometabolomics has the potential to provide early insights into mechanism of drug action and molecular basis for variation in drug response.

The plasma metabolic signatures of ribociclib plus everolimus exposure in patients will be defined using a LC-MS/MS based targeted metabolomics platform, which has been established in the Karmanos Cancer Institute Pharmacology Core ([Bao X, J Clin Pharm, 2019](#)).

We will identify the plasma metabolites that are significantly altered by ribociclib and everolimus exposure, which may provide insights into the mechanism of drug action. In addition, we will explore the associations between the metabolite changes and PK/PD parameters, toxicity, or clinical response. This may help identify potential metabolic biomarkers for the early prediction of clinical outcome.

Pharmacometabolomic samples: No extra sample collection is required for pharmacometabolomic study. Metabolomic profiling will be performed using the plasma PK samples collected at pretreatment and following the combination therapy at 2, 7, and 24 h.

LC-MS/MS based targeted metabolomics: Metabolites in plasma samples will be quantitatively profiled using a LC-MS/MS based targeted metabolomics platform in the Karmanos Cancer

Institute Pharmacology Core, as described previously ([Bao X, J Clin Pharm, 2019](#)). This platform can quantitatively measure about ~250 metabolites that are involved in major human metabolic pathways. All LC-MS/MS analyses were performed on an AB SCIEX QTRAP 6500 LC-MS/MS system. Analyst® 1.6 software was used for system control and data acquisition and MultiQuant 3.0 software was used for data processing and quantitation.

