7.1.1.11.1 Day 1 Enrollment

The following assessments will be performed on Day 1:

- Review of surgical and medical procedures
- ECOG
- 12-lead ECG
- Collection of AEs and Concomitant medication(s)
- Screening assessments not previously collected as noted in section [7.1.1.9](#)
- Day 1 pre-dose PK sample
- Day 1 pre-dose biomarker blood sample
- Confirm eligibility prior to study drug administration
- In clinic/hospital study drug administration
- Provide the patient the following for home dosing on Days 2 and 3
 - Instructions for study medication
 - Dosing Diary
 - Symptom Diary
 - Study drug

7.1.1.11.2 Day 2 and 3

Phase 0 patients will record study drug administration in the Dosing Diary and record symptoms in the Symptom Diary.

7.1.1.11.3 Day 4

The following assessments will be performed on Day 4:

- Review of medical and surgical procedures
- Collection of AEs and Concomitant medication(s)
- Review of home dosing diary and symptom diary

- 12-lead ECG
- Trough PK Sample (Dose Levels 0-3)
- Laboratory testing (may also be performed as a pre-surgical assessment on Day 5 or Day 6):
 - Chemistry, (comprehensive metabolic panel, magnesium, phosphorus)
 - Hematology (CBC w/differential)
 - Coagulation (PT/INR, aPTT)
 - eGFR
- In clinic/hospital study drug administration
- PK blood sampling: 0.5, 1, 2, 4, 7 hours post-dose (Dose Levels 0-3)
 - *In Dose Level 4+ only, PK blood sampling will occur on Day 5 instead of Day 4.*

7.1.1.11.4 **Day 5**

- Review of medical and surgical procedures
- Collection of AEs and Concomitant medication(s)
- 12-Lead ECG (if not collected on Day 4)
- In clinic/hospital study drug administration
- Craniotomy (Day 5 for Cohort 1 & 2; Day 6 for Cohort 3)
 - PK Collection of blood, CSF and tumor
 - Biomarker tumor collection
- Dose Level 1-3: Day 5 trough/24hrs post-dose
- Dose Level 4+ only: PK blood sampling: pre, 0.5, 1, 2, 4, 6, 8 and 24 hours (Day 6) post-dose

7.1.1.11.5 **Follow-up / EOT visit**

Phase 0 patients will have a follow up visit 7-14 days after surgery (routine post-operative visit). All Phase 2 patients should be scheduled for an EOT visit within 7 (± 3) days following discontinuation of study treatment.

The following assessments will be performed at the EOT visit:

- Physical exam
- ECOG performance status
- Weight
- Vital signs
- Laboratory blood collections
 - CMP, magnesium, phosphorus
 - Hematology (CBC w/differential)
 - Urine pregnancy test (if applicable)
- 12-lead ECG

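### At Levels 4-6 the metabolomics plan names a 7 h sample that is not drawn and a 24 h sample taken after or around craniotomy, so surgical effects could be reported as drug effects

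*Combined protocol and SAP*

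**What the plan says.** **Metabolomics samples.** Section 7.1.1.2 takes its metabolite profiles from the PK plasma drawn before treatment and "following the combination therapy at 2, 7, and 24 h". It adds: "No extra sample collection is required for pharmacometabolomic study". The metabolomics time points can therefore come only from the PK schedule.

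**PK schedule, Levels 0-3.** Sections 4.1.1 and 7.1.1.11 place the profile on Day 4, including a 7 h draw. The 24 h sample is the Day 5 trough, taken before that day's dose and before surgery.

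**PK schedule, Levels 4-6.** Section 4.1.1 states: "PK blood sampling will occur on Day 5: pre, 0.5, 1, 2, 4, 6, 8 and 24 hours post-dose". Section 7.1.1.11.3 makes clear that this replaces the earlier profile: "In Dose Level 4+ only, PK blood sampling will occur on Day 5 instead of Day 4". Table 13, note 11, places these draws on "Day 5 (the day of surgery); the 24 hour sample will be obtained on Day 6".

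**Surgery.** Section 4.1.1 sets the time from last dose to craniotomy at 1-3 h in Cohort 1 and 23-25 h in Cohort 3. For the middle group it reads: "Cohort 2: last ribociclib+everolimus dose 7 to 9 hours prior to craniotomy for tumor resection". Section 7.1.1.11.4 puts craniotomy on Day 5 for Cohorts 1 and 2 and on Day 6 for Cohort 3.

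**Analysis.** Section 7.1.1.2 specifies a one-way ANOVA followed by Fisher's LSD. A metabolite is flagged if its FDR-adjusted p-value is below 0.2 and its unadjusted p-value is below 0.05. Flagged changes are attributed to exposure to the two drugs and are then to be related to PK/PD, toxicity and response. The comparison groups are not defined, and there is no term, stratum or exclusion for surgery or dose level.

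**The concern.** Two things go wrong when Section 7.1.1.2 is applied at Levels 4-6. First, one of its three post-dose time points does not exist there. Second, the 24 h point changes meaning: it is a pre-operative sample at the lower levels and a post-operative or peri-operative one at the higher levels.

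The aim is to learn which metabolites the drugs alter. A sample drawn the morning after a craniotomy also reflects anaesthesia, surgery and peri-operative medication. Section 6.3 expects such medication, since it lets anaesthesia staff use otherwise prohibited drugs when clinically necessary. With no element in the analysis to separate these influences, a change caused by surgery would carry the same label as a change caused by the drugs, and the planned associations with PK/PD, toxicity and response would inherit it.

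Surgical status at 24 h also runs alongside the everolimus regimen: 2.5-10 mg daily at Levels 0-3, and a single 50-70 mg dose on Day 5 at Levels 4-6. A difference between the two sets of levels at 24 h could not be assigned to either cause.

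**Working it through.** The plan states no figure for this point, so there is none to reproduce. The check compares schedules and subtracts times.

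**1. Required against collected post-dose times**

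- Required (Section 7.1.1.2): 2, 7, 24 h.
- Collected at Levels 0-3: 0.5, 1, 2, 4, 7, 24 h. Nothing is missing.
- Collected at Levels 4-6: 0.5, 1, 2, 4, 6, 8, 24 h. The 7 h sample is missing.

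Section 7.1 allows ±15 min around 7 h, that is 6.75-7.25 h. The 6 h and 8 h draws are each 1 h away, so neither counts as a 7 h sample. Table 13, note 11, nevertheless describes the Level 4+ times as the same as the others, and the Section 7.1 windows list 7 h but not 6 h or 8 h.

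**2. Sample time relative to planned craniotomy, Levels 4-6**

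If craniotomy is planned between a and b hours after the dose, a sample at t hours falls between t − b and t − a hours after craniotomy. Negative values are before it.

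| Cohort | a-b | 2 h | 6 h | 8 h | 24 h |
|---|---|---|---|---|---|
| 1 | 1-3 h | −1 to +1 | +3 to +5 | +5 to +7 | +21 to +23 |
| 2 | 7-9 h | −7 to −5 | −3 to −1 | −1 to +1 | +15 to +17 |
| 3 | 23-25 h | −23 to −21 | −19 to −17 | −17 to −15 | −1 to +1 |

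For example, Cohort 2 at 24 h: 24 − 9 = 15 and 24 − 7 = 17. The 8 h draw is not a metabolomics point. It is shown because it is the other candidate to replace 7 h, and in Cohort 2 it straddles the planned craniotomy. Induction precedes craniotomy by a time the documents do not give, so the 6 h sample in Cohort 2 may or may not be pre-induction.

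**3. Who is affected at Levels 4-6**

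- Under Section 4.1.1, the 3 to 6 escalation patients per level are all in Cohort 2, so every 24 h sample follows craniotomy.
- Section 6.4.2 requires, at each dose level, at least one patient in each time cohort. With 3 patients, 2 samples follow craniotomy and 1 (Cohort 3) is within about 1 h of it.
- If a level is expanded by 4 patients in each of Cohorts 1 and 3, and escalation was all in Cohort 2, (6 + 4) of (6 + 4 + 4) = 10 of 14 follow craniotomy, or (3 + 4) of (3 + 4 + 4) = 7 of 11. The other 4 are peri-operative.

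**4. Could the planned rule pick up a surgical effect?**

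This is an illustration only. Its assumptions are not in the documents: 250 independent metabolites, three groups (pretreatment, 2 h, 24 h), no drug effect, and surgery shifting 30% of metabolites at 24 h in every patient. Share of shifted metabolites flagged by the plan's rule:

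| Patients per group | 1 SD | 1.5 SD | 2 SD |
|---|---|---|---|
| 3 | 1% | 6% | 30% |
| 6 | 15% | 66% | 91% |

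With no shift, fewer than one metabolite in total is flagged on average. The rule can therefore flag purely surgical changes, but how many depends almost entirely on an unknown effect size and on the number of patients. Mixing in pre-operative 24 h samples would dilute the effect.

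**The case against.** The best defence is that this is an exploratory objective, described as hypothesis-generating and run with a lenient FDR. No dose decision, Phase 2 entry rule, or primary or secondary endpoint uses it. The missing 7 h point can be seen as a drafting slip, and the 24 h problem can be handled at analysis because Section 6.1.4.2 requires dosing and sampling times to be recorded precisely. All of that stands and limits how serious the point is. It does not remove it: Section 9.6.1 says no separate SAP will be issued, so no later document is planned in which the handling would be settled.

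Three stronger readings are tempting, and the documents do not support them.

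- *Surgical effects will be read as the drug signature.* The documents give no size for any surgical effect on these metabolites. What can be said is that such effects could be reported as drug effects and that the plan has no means of telling them apart.
- *A fixed share of all 24 h samples is contaminated.* One could take the minimum numbers in Table 7, 6 + 3 + 3 + 3 = 15 at Levels 0-3 and 3 × 3 = 9 at Levels 4-6, and report 9 of 24 (38%). That requires all seven levels to open, dose levels to be pooled, which the plan does not say, and the Section 4.1.1 assignment to prevail. Under Section 6.4.2 it would be about 6 of 24 (25%), and if escalation stops below Level 4 it is zero. Filling Level 6 to 6 patients and expanding it by 8 gives 16 of 35 (46%), but 35 exceeds the maximum of 32 stated in Section 9.7.1.
- *Section 7.1.1.2 was simply left behind when Levels 4-6 were added.* This is plausible, but the superseded text is not available to show it.

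Nor does analysing dose levels separately escape the problem. The Level 4-6 24 h group would then consist of post-operative or peri-operative samples, with nothing pre-operative by design to compare at that time.

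**Conclusion.** The point holds. As written, Section 7.1.1.2 cannot be followed at Levels 4-6 for the 7 h sample. Its 24 h result there cannot be attributed to the drugs in Cohorts 1 and 2, and is doubtful in Cohort 3. Surgery and everolimus regimen are confounded at 24 h whether or not levels are pooled.

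The timing conclusions assume that dosing, sampling and craniotomy keep to their planned intervals. The direction of the weakness is clear. The size of the bias is not given by the documents, and the number of patients affected cannot be fixed until it is known which levels open and whether Section 4.1.1 or Section 6.4.2 governs cohort assignment. The consequence is confined to an exploratory objective, but the repair is cheap enough that it should be made.

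**What to change.** Amend Section 7.1.1.2 as follows.

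1. Restrict the drug-exposure signature to samples drawn before induction of anaesthesia, using the recorded sampling times. The induction time must also be available to the analyst.
2. At Levels 4-6, replace the 7 h point with the scheduled 6 h sample where it is pre-induction, which is expected mainly in Cohorts 2 and 3.
3. Analyse post-induction samples separately, labelled peri-operative or post-operative. At Levels 4-6 these are all 24 h samples in Cohorts 1 and 2, the 6 h sample in Cohort 1, and any 2 h Cohort 1, 6 h Cohort 2 or 24 h Cohort 3 sample that proves to have been drawn after induction.
4. Do not pool those samples with the 24 h samples of Levels 0-3.
5. Define the ANOVA comparison groups, and reconcile Sections 4.1.1 and 6.4.2 on cohort assignment.

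The cost is wording: every sample is already scheduled and treatment does not change. The losses should be stated openly. There will be no clean 24 h signature for Cohorts 1 and 2 at Levels 4-6, possibly no clean post-dose metabolomics point at all in Cohort 1 at an expanded level, and a 6 h against 7 h mismatch between the two sets of levels.

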Metabolomic data analysis: Metabolomics data analyses were performed using the MetaboAnalyst web-based statistical package (<http://www.metaboanalyst.ca/>). Features (i.e., Metabolites) with >50% missing values were removed from the analysis, and the remaining missing values were replaced by the minimum value of a feature. To meet the normality assumption, individual metabolite concentrations were log-transformed and then auto-scaled (mean-centered and divided by the standard deviation of each metabolite). A one-way analysis of variance (ANOVA), if significant, followed by Fisher's LSD post-hoc analysis was performed to identify significantly changed metabolites among groups. The study of metabolic signature of the drug exposure in patients was intended to be hypothesis-generating and thus a false discovery rate (FDR) adjusted p-value < 0.2 along with unadjusted p-value < 0.05 was used to identify plasma metabolites significantly changed. A heat map was used to visualize metabolic signatures of ribociclib plus everolimus exposure, with significantly changed metabolites ranked in ascending order according to the FDR adjusted p-values from the ANOVA test.

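### Read as pooling all time points, the 50% missing-value filter deletes metabolites that fall to undetectable after dosing and keeps the mirror-image rises

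*Combined protocol and SAP*

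**What the plan says.** Section 7.1.1.2 (Pharmacometabolomics) profiles "plasma PK samples collected at pretreatment and following the combination therapy at 2, 7, and 24 h", which is one sample before treatment and three after. The paragraph on metabolomic data analysis then sets the filter: "Features (i.e., Metabolites) with >50% missing values were removed from the analysis". For metabolites that pass, "the remaining missing values were replaced by the minimum value of a feature". Testing follows: "A one-way analysis of variance (ANOVA), if significant, followed by Fisher's LSD post-hoc analysis was performed". A metabolite is called changed at "a false discovery rate (FDR) adjusted p-value < 0.2 along with unadjusted p-value < 0.05".

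The aim has no direction: "We will identify the plasma metabolites that are significantly altered by ribociclib and everolimus exposure". The work "was intended to be hypothesis-generating", and sections 3 and 9.6 list it as exploratory.

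At the higher dose levels the draws differ. Section 4.1.1 says for Dose Level 4+ that "PK blood sampling will occur on Day 5: pre, 0.5, 1, 2, 4, 6, 8 and 24 hours post-dose". Of the four metabolomic times, only pre-dose, 2 h and 24 h exist there.

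No other section deals with missing metabolite values, and section 9.6.1 says that no separate SAP will be issued.

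**The concern.** The filter counts missing values per metabolite without regard to when the sample was taken, and post-dose samples outnumber pre-dose samples three to one. If values are missing because they lie below the detection limit, the chance of passing the filter depends on the drug effect and on its direction.

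Replacing missing values with the minimum shows that the plan itself treats missing as low. The filter can therefore discard what the next step would have read as a large decrease. The loss is silent: a deleted metabolite never reaches the ANOVA, the FDR step or the heat map, and a lenient FDR threshold cannot bring it back. At stake is the completeness of an exploratory signature of two inhibitors, for which decreases are a plausible finding.

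**Working it through.** The documents give no sample size, power or error rate for the metabolomics, so there is no planned figure to reproduce.

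**Step 1: the filter applied to the sampling schedule (section 7.1.1.2; section 4.1.1 for Level 4+).** Let m_pre and m_post be the missing shares before and after dosing.

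- Four times: pooled missing = 0.25 × m_pre + 0.75 × m_post.
- Level 4+ (pre, 2, 24 h): pooled missing = (1/3) × m_pre + (2/3) × m_post.

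| Pattern | Four times | Level 4+ times |
|---|---|---|
| Always detected pre-dose, never post-dose | 3/4 = 75%, deleted | 2/3 = 66.7%, deleted |
| Never detected pre-dose, always post-dose | 1/4 = 25%, kept | 1/3 = 33.3%, kept |
| Fall, undetectable at two of three post-dose times | 2/4 = 50%, kept | not applicable |
| Rise, detected at one post-dose time only | 3/4 = 75%, deleted | 2/3 = 66.7%, deleted |

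**Step 2: the boundary.** With m_pre = 0, deletion needs 0.75 × m_post > 0.5, so m_post > 2/3. With three times it needs (2/3) × m_post > 0.5, so m_post > 3/4. A fall that stays above the detection limit has m_post = 0 and is never touched.

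Steps 1 and 2 assume only a pooled denominator.

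**Step 3: how often this could happen.** Assumptions, none of them in the documents: log-normal concentrations with SD 0.8 on the natural-log scale, independent samples, the same fall at all three post-dose times, and 12 or 24 patients (section 9.7.1 gives 6 to 32 for Phase 0). Let b be the share of baseline values below detection. Then m_post = Φ(Φ⁻¹(b) + ln(fold)/0.8). For a 4-fold fall and b = 10%: Φ(−1.282 + 1.733) = 0.674, and pooled missing = 0.25 × 0.10 + 0.75 × 0.674 = 0.531. The expected share is just above the cut-off.

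| Fall | b | m_post | Expected pooled missing | Deleted, 12 / 24 patients |
|---|---|---|---|---|
| 4-fold | 10% | 0.674 | 0.531 | about 64% / 71% |
| 4-fold | 5% | 0.535 | 0.414 | 7% / 2% |
| 4-fold | 2% | 0.374 | 0.286 | 0% / 0% |
| 5-fold | 10% | 0.767 | 0.600 | about 94% / 99% |
| 5-fold | 5% | 0.643 | 0.495 | about 41% / 42% |
| 5-fold | 2% | 0.483 | 0.367 | 1% / 0.1% |

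The mirror-image rise at b = 10% has expected pooled missing of 0.25 × 0.674 + 0.75 × 0.10 = 0.244 (4-fold), well below the cut-off, and is deleted in essentially no runs.

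**Step 4: does a within-time-point filter cure it?** Rule tested: keep a metabolite detected in at least 50% of samples at one or more time points. In a separate simulation (SD 1 on the log scale, detection limit midway between the pre- and post-dose means, a 2-SD fall, minimum-value replacement, ANOVA at unadjusted p < 0.05), the fall is kept in 99% of runs with 6 patients and 99.9% with 12. It reaches p < 0.05 in 80% and 99%. Under the pooled filter it reaches p < 0.05 in 2% and 0.3%, because it is deleted in 97% and 99.7%.

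**Step 5: the price.** Retention now uses the time labels that are then tested. For metabolites with no drug effect, 12 patients and 70% to 80% missing, the false-positive rate among those retained is about 7% to 17% under ANOVA with minimum-value replacement. At 70% missing about 39% are retained, so the rate over all such null metabolites is about 0.39 × 0.08 = 3%. At 80% missing about 7% are retained, giving about 0.07 × 0.17 = 1%. Both are below 5%.

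**The case against.** Five points can fairly be made against this.

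- **The denominator is not written out.** The section describes an established platform in the past tense, and its laboratory may already filter within time point. Falls and rises would then be treated alike. This stands: the point is conditional on the pooled reading, which is the plain one but not the only one.
- **The effect is narrow.** A reader might infer that the rule removes the strongest decreases and keeps the increases. The documents do not support that. Deletion depends on closeness to the detection limit, not on the size of the fall: a 10-fold fall in an abundant metabolite is kept. Some rises are deleted too, as Step 1 shows. Nothing in the protocol says that any of the roughly 250 targeted metabolites lies near its limit.
- **The simulated frequencies rest on an assumed input.** Quoting only the rows with 10% of baseline values below detection would suggest deletion in 64% to 99% of runs. At 2% the problem all but vanishes. This stands, so the range has to be shown.
- **The alternative filter has its own cost.** It selects on the labels under test. This also stands, but the rate per null metabolite stays below 5% in the settings tested, so it is a cost to disclose and not a reason to keep the pooled rule.
- **The analysis is hypothesis-generating.** Section 9.6.1 lets exploratory analyses change if the change is reported. This limits the importance of the point. It does not make the filter suit the section's own aim.

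**Conclusion.** The concern holds in a limited form. If the filter pools time points, it treats a sustained fall to undetectable differently from its mirror image: 75% missing and deleted against 25% and kept, or 66.7% against 33.3% with the Level 4+ times. That follows from the schedule and needs no distributional assumption. It affects only metabolites that drop below detection in more than two-thirds of post-dose samples (three-quarters with three times), given full baseline detection.

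How many metabolites would be lost cannot be determined from the documents. Under the stated assumptions the answer runs from none to nearly all such falls as the baseline share below detection moves from 2% to 10%. A general bias of the whole signature towards increases is not shown. No primary or secondary endpoint depends on this analysis, so the change is a cheap improvement and not a necessity.

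**What to change.** In section 7.1.1.2, state the denominator and apply the filter within time point: keep a metabolite detected in at least 50% of samples at one or more time points. If the laboratory already does this, saying so settles the point.

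For metabolites that the pooled rule would have removed, use a paired pre/post comparison of detection frequency (McNemar or Cochran Q, chosen in advance) as their single test in the FDR family. It should replace the ANOVA for these metabolites, not add a second test. Flag them in the results as sparse, and state that their false-positive rate is above nominal because retention used the time labels.

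The cost is a sentence or two of text, a larger FDR family (the platform caps it at about 250 metabolites) and a small amount of analysis work. No new samples or assays are needed.

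The same edit should reconcile the 7 h metabolomic sample with the Level 4+ sampling times in section 4.1.1, Table 13 and section 7.1.1.11.4, which list 6 h and 8 h but no 7 h.
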